### The 2 scan intervals are defined as below:

The 2 scan interval from following treatment start date is 119 days (= 16 weeks + 7 days)

If the previous adequate tumor scan (prior to PD) was prior to 365 days, the 2 scan interval is defined as 126 days (= 16 weeks + 14 days)

If the previous adequate tumor scan (prior to PD) was on or after 365 days but prior to 469 days (= 68 weeks - 7 days), the 2 scan interval is 154 days (= 20 weeks + 14 days)

If the previous tumor scan (prior to PD) was after 469 days, the 2 scan interval is 182 days (= 24 weeks + 14 days)

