**Figure 2: AIM-HN Design**

All subjects must have measurable disease that meets the criteria for selection as a target lesion according to RECIST v1.1 and presence of at least measurable target lesion by local radiology prior to enrollment is required. HNSCC diagnosis will be by local laboratory. All AIM-HN enrolled subjects must have a known missense HRAS tumor mutation based on centralized testing or other HRAS test used by the trial site that has been approved by Kura Oncology, Inc.

AIM-HN enrolled subjects will receive treatment with tipifarnib until disease progression, unacceptable toxicity or any criteria for withdrawal from the trial or treatment occurs. Tipifarnib will be administered with food at a starting dose of 600 mg, orally, bid on days 1-7 and 15-21 of 28-day treatment cycles. Stepwise 300 mg dose reductions to control treatment-related, treatment-emergent toxicities may occur.

Tumor assessment for the primary analysis will be performed by IRF according to RECIST v1.1 and provided to the IDMB. Investigator assessment of tumor response will also be collected and reported as a supportive analysis. Tumor response assessment should occur approximately every 8 weeks ( $\pm 5$  days) for the first 12 months; thereafter, tumor response assessment should occur approximately every 12 weeks ( $\pm 5$  days) until disease progression. The tumor response assessment schedule (every 8-12 weeks) should be maintained regardless of dosing delays or additional imaging assessments performed. Upon disease progression, all subjects will be followed approximately every 12 weeks for survival and the use of subsequent therapy until either death or End of Study (up to 2 years after the enrollment of the last study subject, see [protocol Section 6.7.1](#)), whichever occurs first. All subjects will be followed-up for safety through the End of Treatment visit which occurs approximately 30 days after treatment discontinuation or immediately before the administration of another anticancer treatment, whichever occurs first. Additional safety follow-up may be conducted if unresolved toxicity is present at this End of Treatment visit.

[figure not shown]

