## 7.3 Efficacy Variables

The primary efficacy measure is anti-tumor response assessed by an IRF every 8 weeks in the first 12 months of study treatment and every 12 weeks thereafter until disease progression. Assessments will also be made by the Investigator. Response criteria will be based on RECIST v1.1. Baseline efficacy assessments are required to be completed within 28 days prior to Cycle 1 Day 1. Any tumor assessment completed within 42 days prior to Cycle 1 Day 1 will be considered as baseline assessment.

The following variables are defined for AIM-HN only. Efficacy variables will be reported for the High VAF subjects as well as all VAF subjects.

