### 7.3.3 Duration of Response (DOR)

DOR (months) is defined as the time from the date of first response (CR or PR) to the date of progression of disease or death of any cause, whichever occurs first, in patients with a confirmed CR or PR, i.e., (date progression of disease or death – date of first CR or PR + 1)/30.4375.

The censoring rules for DOR is identical to it for PFS as specified in [Table 1](#).

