**Table 1 PFS Censoring Rules**

Hierarchy Censoring	Situation	Date of Event or Censor	Event / Censor
1	No baseline radiological tumor assessment (confirmed measurable disease per RECIST v1.1) available	Treatment start date	Censor
5	No post baseline tumor assessment available and no death reported within 2 scan intervals following treatment start date	Treatment start date	Censor
	No post baseline tumor assessment available but death reported within 2 scan intervals following treatment start date	Date of death	Event
6	No tumor progression and no death reported within 2 scan intervals following last adequate tumor assessment	Date of last adequate assessment	Censor
	No tumor progression but death reported within 2 scan intervals following last adequate tumor assessment	Date of death	Event
	Tumor progression documented within 2 scan intervals following previous adequate tumor assessment	Date of progression	Event
3	Tumor progression documented after 2 scan intervals following previous adequate tumor assessment	Date of previous adequate assessment	Censor
2	New anticancer treatment started and no tumor progression	Date of previous adequate assessment prior to new therapy	Censor
4	No tumor progression and patient lost to follow-up or withdrawal of consent	Date of last adequate assessment	Censor

Notes: Adequate tumor assessment refers to a baseline assessment or a post-baseline assessment with an overall response of CR, PR, SD, non-CR/non-PD, or PD.

If target, non-target, and new lesion assessments have different dates within a visit, then the earliest of those dates will be considered as the date of the tumor assessment if the assessment for that visit is PD; otherwise, the latest date will be used.

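### SAP 7.3.4 lengthens its two-scan windows one scan too late, so around month 12 a progression found after a single missed scan is censored in PFS and DOR

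*SAP*

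**What the plan says.** SAP 7.3 has tumours "assessed by an IRF every 8 weeks in the first 12 months of study treatment and every 12 weeks thereafter until disease progression", and SAP 5.1 repeats that "thereafter, tumor response assessment should occur approximately every 12 weeks", with ±5 days on each scan. The schedule is to be kept regardless of dosing delays or extra imaging.

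SAP Table 1 (section 7.3.4) censors at the previous adequate assessment when progression is "documented after 2 scan intervals following previous adequate tumor assessment". The notes below the table give the window lengths in three bands:

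- The first band covers a scan earlier than day 365. Its window is 126 days, made up of 16 weeks and a 14-day allowance.
- The middle band is introduced by "If the previous adequate tumor scan (prior to PD) was on or after 365 days but prior to 469 days". Its window is 154 days, made up of 20 weeks and the same allowance. The SAP explains day 469 as 68 weeks minus 7 days.
- The last band reads "If the previous tumor scan (prior to PD) was after 469 days, the 2 scan interval is 182 days". This length is made up of 24 weeks and the same allowance.

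SAP 7.3.3 carries this over: "The censoring rules for DOR is identical to it for PFS as specified in" Table 1. Protocol 12.1.1 has a different DOR rule, under which progression is censored only when more than one assessment visit has been missed. For PFS the protocol gives a flat 126-day window and applies it to deaths.

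**The concern.** A two-scan window has to cover the two intervals that follow the previous adequate scan. The SAP's lengths (16, 20 and 24 weeks, plus slack) are the right set for an 8-to-12-week switch, but each longer window seems to start one scan after it is first needed. If so, the rule tolerates one missed scan everywhere except around month 12, and no reason is given for treating that period differently.

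Each affected subject would lose a documented progression in PFS and in DOR, and DOR is a key secondary endpoint. These subjects are long responders or long-term progression-free, so they shape the tail of the Kaplan-Meier curve. A scan read as not evaluable has the same effect as a missed one, because the Table 1 notes do not count it as adequate.

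**Working it through.** **1. The SAP's own figures.** 16×7+14 = 126; 20×7+14 = 154; 24×7+14 = 182; 68×7−7 = 469. All agree with the text, so the lengths are computed correctly. The question is which scans they are attached to.

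**2. The calendar.** No section lists the scan weeks. Week 68 can be 12 weeks after an 8-week scan only if that scan is week 56 (56+12 = 68, whereas 48+12 = 60). The SAP's cut-point therefore implies 48/56/68/80/92. Week *w* is taken as day 7*w*.

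**3. Required against given.** Required window = days to the second next scheduled scan + the SAP's 14 days.

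| Last adequate scan | Missed | PD found | Gap (days) | Gap with ±5 days per scan | Required | SAP window | Result |
|---|---|---|---|---|---|---|---|
| Weeks 8 to 40 | next | second next | 112 | 102–122 | 126 | 126 | event |
| Week 48 (day 336) | 56 | 68 (day 476) | 140 | 130–150 | 154 | 126 | censored |
| Week 56 (day 392) | 68 | 80 (day 560) | 168 | 158–178 | 182 | 154 | censored |
| Weeks 68, 80 | next | second next | 168 | 158–178 | 182 | 182 | event |

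Each scan can shift by −5 to +5 days, giving 11×11 = 121 combinations. In the two failing rows even the shortest gap exceeds the window (130 > 126; 158 > 154), so progression is lost in 121 of 121. In the other rows the longest gap fits (122 < 126; 178 < 182), so it is lost in 0 of 121.

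**4. The other natural calendar, 48/60/72/84.** Three positions fail, each in 121 of 121: 40→60 (gap 140, window 126), 48→72 (168 against 126) and 60→84 (168 against 154).

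**5. Effect on one subject's DOR.** Take a response first seen at week 8 (day 56) and the SAP formula.

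- PD at week 68: (476−56+1)/30.4375 = 13.8 months, event. It becomes (336−56+1)/30.4375 = 9.2 months, censored.
- PD at week 80: (560−56+1)/30.4375 = 16.6 months, event. It becomes (392−56+1)/30.4375 = 11.1 months, censored.

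**6. Effect on a curve (illustration with assumed inputs).** Suppose N subjects are at risk at day 336 on the PFS axis. One is affected, two others progress at day 392, and nothing else happens. Values are fractions of the day-336 estimate.

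| N | PD kept, days 392–475 | PD kept, from day 476 | SAP rule, from day 392 |
|---|---|---|---|
| 10 | 8/10 = 0.800 | 0.800×7/8 = 0.700 | 7/9 = 0.778 |
| 20 | 18/20 = 0.900 | 0.900×17/18 = 0.850 | 17/19 = 0.895 |

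The SAP curve is slightly low before the lost progression, because the subject has left the risk set, and too high after it.

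**7. What does not change.** Nine months is 9×30.4375 = 273.9 days. The earliest wrongly used censoring date is day 336−5 = 331, or 280−5 = 275 on the second calendar. The 6- and 9-month PFS rates are therefore untouched. ORR and OS do not use these windows.

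**8. Day 469.** One band ends before day 469 and the next begins after it, so a scan on that day has no window.

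**The case against.** - **The calendar is inferred.** This is true. If 8-week scans ran on to week 64, only one position would fail (last scan week 64, gap 168, window 154), and neither example in the table above would arise. But that calendar conflicts with 12-weekly scanning after 12 months, and it still fails once. No calendar tried is free of the fault.
- **The 126-day figure is the protocol's own.** The protocol describes it as roughly two assessment intervals, but uses it for PFS deaths, not progression. For PFS deaths after a post-baseline scan the SAP is at least as lenient, so no harm is claimed there. It is also true that no document says in words that PFS must tolerate exactly one missed scan. That principle is explicit only in the protocol's DOR rule, and for PFS it is read from how the windows behave everywhere else.
- **The DOR departure may be declared.** Part of SAP section 3 is redacted, so a conflict with the protocol cannot be asserted outright. Disclosure would not correct the arithmetic.
- **The effect is small.** This largely stands. A subject must be progression-free at about 11 to 13 months (about 9 to 14 on the second calendar), miss one scan, and have no unscheduled, End of Treatment or follow-up scan that shortens the gap (protocol 10.1.2, 9.2.7, 9.2.8). The endpoints concerned are summarised descriptively, the protocol plans PFS sensitivity analyses, and the SAP provides listings with its tables. A shift in median PFS is not a realistic expectation: it would need a curve near 0.5 at about day 392 to 476, and nothing in the documents supports that with at least 80 subjects planned.
- **Day 469 is trivial.** It is: an in-window week-68 scan falls on days 471 to 481. It should simply be tidied in the same edit.

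**Conclusion.** The concern holds. On the calendar the SAP implies, the windows after weeks 48 and 56 are each 28 days shorter than the SAP's own construction requires (154−126 and 182−154), and a single missed scan there always turns a documented progression into a censored observation. The exact weeks rest on the inferred calendar. The existence of the fault does not, because a scheduled scan in the day 365–468 band that is followed by two 12-week intervals needs more than 154 days on any reading.

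The consequence is confined to the later part of the PFS and DOR curves. The number of affected subjects cannot be derived from the documents and is probably small, since the SAP reports early closure with limited data. It does not threaten the primary endpoint, but it should be corrected before event status is fixed.

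**What to change.** State the scan weeks across the switch in SAP 7.3.4 and key the existing window lengths to them.

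| Window | Previous adequate scan, calendar 48/56/68/80 | Previous adequate scan, calendar 48/60/72 |
|---|---|---|
| 126 days | before day 329 (48×7−7) | before day 273 (40×7−7) |
| 154 days | day 329 to before day 385 (56×7−7) | day 273 to before day 329 |
| 182 days | day 385 or later | day 329 or later |

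On its own calendar each set keeps every progression found after one missed scan: the longest gaps are 122, 150 and 178 days against 126, 154 and 182. Each set still censors every progression after two missed scans; the shortest such gap in the first band, for example, is 168−10 = 158 days against 126. Either set also gives day 469 a window.

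Apply the same windows to PFS and DOR. Unless a redacted item already does so, record in SAP section 3 any departure from the protocol's DOR rule and from its 126-day PFS death window. The second matters because the longer windows would count some deaths beyond 126 days as events.

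The cost is three lines in SAP 7.3.4, a sentence in section 3 and a change to the derivation program, all before database lock and without new data. Any affected subjects move from censored to event, which lowers the curves slightly after the progression date and raises them slightly just before it.

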### 7.3.5 Overall Survival (OS)

OS (months) is defined as the time from first dose date until death from any cause, i.e., (date of death – date of first dose date + 1)/30.4375. Patients who are still alive at the time of the final analysis data cutoff,

or who have become lost to follow-up will be censored at their last known to be alive date on or before the date of data cutoff. Last known alive dates will come from the Survival Status CRFs.

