Serum chemistry ¹⁷	X ¹⁰	X ¹¹	X ¹⁸		X		
Hematology ¹⁷	X ¹⁰	X ¹¹	X ¹⁸		X		
Coagulation ¹⁷	X ¹⁰						
Urinalysis ¹⁹	X ¹⁰						
Radiographic Imaging, transfer of tumor scans and related clinical data to IRF ²⁰	X ¹³			X ²¹	X ²²	X ²³	
Tumor tissue for HRAS mutational testing and pathology confirmation at a central lab ^{31, 32}	X						

Tipifarnib administration ²⁸		X					
Drug accountability and diary review		X ¹⁶			X		
Collection of survival and anticancer treatment information ²⁹							X
QoL questionnaires ³⁴	X	X			X		

1. Screening evaluations will be completed within 4 weeks (28 days) of Cycle 1 Day 1. Evaluations performed as part of the standard of care within 28 days of dosing (prior to study specific consent signature) do not need to be repeated.
2. Tumor response assessment should occur approximately every 8 weeks (± 5 days) for the first 12 months of a subject's participation in AIM-HN; thereafter, tumor response assessment should occur approximately every 12 weeks (± 5 days) until disease progression.
3. An End of Treatment visit will be conducted approximately 30 days (± 7 days) from the last dose of tipifarnib or immediately before the initiation of any other anticancer therapy, whichever occurs first.
4. Follow up visit required only for subjects who terminated treatment for reasons other than disease progression and should occur approximately every 8 or 12 weeks (± 5 days) until disease progression.
5. Demographics and disease history including primary diagnosis (date of initial diagnosis, stage of disease at diagnosis, anatomical disease site(s) at diagnosis), current stage of disease, smoking and betel nut exposure history, alcohol use, HPV status and other relevant medical history.
6. Prior anti-cancer therapy for HNSCC including name, dates (start, end), treatment outcome (response and response criteria), duration of response, date of progression. Additionally, information will be collected specific to first line systemic treatment for recurrent or metastatic HNSCC. Information will also be collected on prior cancer surgery for HNSCC including date(s) of surgery. Information will be collected on prior/current radiological treatments for HNSCC including anatomical site(s) and date(s) of radiation treatment.

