29. Upon disease progression, follow up contact with the subject and/or caregiver(s) (e.g. electronic technology-based, telephone or in person) is to occur approximately every 12 weeks (\pm 1 week) for survival and the use of subsequent therapy until either death or End of Study (up to 2 years since the enrollment of the last study subject in AIM-HN, see [Section 6.7.1](#)), whichever occurs first. Information on survival and subsequent anticancer therapy for HNSCC will be collected including name, dates (start, end), treatment outcome (response and response criteria), duration of response, date of progression. Information will also be collected on subsequent cancer surgery(ies) for HNSCC including date of surgery. Information will be collected on subsequent radiological treatments for HNSCC including anatomical site(s) and date(s) of radiation treatment.

[REDACTED]

[REDACTED]

31. Tumor tissue for central review/confirmation, preferably from the same tissue sample used for Pre-screening HRAS mutational testing, must be confirmed as available prior to Cycle 1 Day 1 of AIM-HN. Whenever possible, sample should be sent to Sponsor (or designee) prior to Cycle 1 Day 1.
32. Detailed tumor sample collection, storage and shipping procedures will be provided in a separate lab manual.

[REDACTED]

34. EORTC QLQ-H and N35 and EQ-5D-5L ([Appendix III](#)) quality of life questionnaires will be completed at baseline, monthly on treatment, and at the End of Treatment visit.

Table 3: Schedule of Events: SEQ-HN

Activity	Screening ¹	Study Enrollment ¹	On Study Visit: 16 – 24 weeks since enrollment in SEQ-HN or at disease progression, whichever occurs first ²	Follow Up Contacts
ICF for participation in SEQ-HN	X			
Inclusion/ exclusion criteria evaluation	X			
Demographics and disease history ⁴		X		
Prior anti-cancer therapy for HNSCC ⁵		X		X

1. Screening and study enrollment may occur during the same visit.
2. On study visit is to occur between weeks 16 – 24 from the subject’s enrollment in SEQ-HN. If a subject experiences disease progression or initiates second line therapy prior to weeks 16 - 24, the blood sample for HRAS mutational analysis should be collected at that time.

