9.2.9 Follow Up Contact

Upon disease progression or withdrawal of consent for additional study procedures, follow up contact with the subject and/or caregiver(s) (e.g. electronic technology-based, telephone or in person) is to occur approximately every 12 weeks (\pm 1 week) for survival and the use of subsequent therapy until End of Study (see [Section 6.7.1](#)). Information on survival and subsequent anticancer therapy for HNSCC will be collected including name, dates (start, end), treatment outcome (response and response criteria), duration of response, date of progression. Information will also be collected on subsequent cancer surgery(ies) for HNSCC including date of surgery. Information will be collected on subsequent radiological treatments for HNSCC including anatomical site(s) and date(s) of radiation treatment.

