## 2 Scope

This SAP supplements the study protocol and provides more details on the strategy, rationale, and statistical techniques to be used towards achieving the study objectives.

The SAP outlines the following:

[figure not shown]
- Study objectives
- Study design
- Variables analyzed and analysis sets
- Applicable study definitions
- Statistical methods regarding important protocol deviations, study drug exposure, efficacy analysis, concomitant medications, adverse events handling, laboratory data and physical examinations

See [Appendix 1](#) for a list of abbreviations used throughout this document. The list of the mock tables, figures, and listings depicting the analyses described in this SAP are presented in a separate document.

This SAP should be read in conjunction with the study protocol and case report form (CRF). This version of the plan has been developed using the protocol v3.0 dated 09JUN2020 and CRF v6.0 dated 11Nov2022. Any changes to the protocol may necessitate updates to the SAP.

The final version of the SAP will be issued for sponsor approval prior to database lock. Any deviations from the final version of the SAP will be documented in the final Clinical Study Report (CSR).

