### 7.3.4 Progression-free Survival (PFS)

PFS (months) is defined as the time from the first dose of the study drug to the first documented disease progression (PD) or death, whichever comes first. If a patient has not progressed or dies at the time of interim or final analysis (up to the date of data cutoff), PFS will be censored on the date of the last tumor assessment (up to the data cutoff). The censoring rules and censoring hierarchy for PFS is specified in [Table 1](#).

The PFS time will always be derived based on the tumor scan dates, not the assessment dates or visit dates.

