## 9.8.2 Deaths

Death data from the survival status CRF will be summarized in a table and presented in a listing. Causes of death will be included.

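### OS last-known-alive dates are tied to one CRF with no fallback, so OS could be censored before PFS in the same subject (minor)

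*SAP*

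**What the plan says.** SAP 7.3.5 censors OS at the last known alive date, on or before data cutoff, for subjects still alive and for those lost to follow-up. On the source of that date it says: "Last known alive dates will come from the Survival Status CRFs". No second source appears. The only other contact-date rule, in SAP 8.1.1, caps imputed stop dates for adverse events and concomitant medications and is not linked to OS.

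The form is named in one other place, SAP 9.8.2: "Death data from the survival status CRF will be summarized in a table". Neither section says when it is completed.

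In Protocol Table 2 the row "Collection of survival and anticancer treatment information" has a single mark, which reads as the Follow Up Contact column. Footnote 29 and SAP 5.1 start that contact at progression, about every 12 weeks. Protocol 9.2.9 is slightly wider: "Upon disease progression or withdrawal of consent for additional study procedures, follow up contact with the subject". The visible assessment lists for treatment visits, tumor assessments, the End of Treatment visit and the pre-progression Follow up Visit (Protocol 9.2.2 to 9.2.8) contain no survival-status item.

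PFS does not depend on this form for its censoring date. Under SAP 7.3.4, for a subject without progression or death, "PFS will be censored on the date of the last tumor assessment (up to the data cutoff"). Table 1 also covers subjects lost to follow-up without progression.

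**The concern.** Read literally, a progression-free subject may have no Survival Status record, or only an old one, while dosing, laboratory, scan and questionnaire records show the subject alive much later. PFS would then run to the last scan and OS would stop earlier, or have no date at all. That is logically impossible, because a subject scanned on a given day was alive on that day.

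The error also has a direction. The exposed subjects are mainly those still progression-free at cutoff, who are doing best. Deaths in the same group are still counted, so shortening or dropping only the survivors' follow-up pulls the OS curve down.

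What is at stake is the descriptive OS curve, median OS and the 12-month OS rate. ORR does not use this date, and SAP 7.3.3 gives DOR the PFS censoring rules.

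**Working it through.** The plan gives no figure to reproduce. The check has two parts.

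**1. Can the rule as written put OS before PFS?** Yes. The OS date comes from a form whose only visible schedule starts at progression or withdrawal of consent for procedures. The PFS date comes from scans every 8 weeks for 12 months, then every 12 weeks. Take a progression-free subject with a last form 8 weeks before cutoff and a last scan 3 weeks before: OS is censored 8 − 3 = 5 weeks earlier than PFS.

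**2. How much could it matter?**

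From the documents: median OS of 5 to 8 months in second line (Protocol 4.3); study end 2 years after the last AIM-HN enrolment (Protocol 6.7.1); the scan schedule.

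Assumed: n = 60; uniform accrual over 36 months; exponential PFS and post-progression survival (PPS); 10% of PFS events are deaths; cutoff F = 0, 3, 6, 12 or 24 months after last entry.

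Expected number progression-free at cutoff, with median PFS m and accrual A:

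N = n × m / (A ln 2) × [2^(−F/m) − 2^(−(F+A)/m)]

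- m = 2.5: the leading factor is 60 × 2.5 / (36 × 0.693) = 6.0. This gives about 6.0 subjects at F = 0, 1.1 at F = 6 and 0.01 at F = 24.
- m = 4: the leading factor is 60 × 4 / (36 × 0.693) = 9.6. This gives about 9.6, 3.4 and 0.15.

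These counts explain why any effect is confined to early cutoffs.

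The Kaplan-Meier estimate is S(12) = ∏(1 − d_j / n_j) over death times up to 12 months. Removing a living subject early lowers n_j and leaves d_j unchanged, so S(12) falls. Fall in 12-month OS, in percentage points, over 2,000 simulated trials per setting, at F = 0 / 3 / 6 / 12 / 24:

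| Median PFS, PPS (median OS), months | (a) last form uniform 0–12 weeks before cutoff | (b) no form, date missing |
|---|---|---|
| 2.5, 3 (6.2) | 0.4 / 0.3 / 0.2 / 0.0 / 0.0 | 1.4 / 1.2 / 0.8 / 0.3 / 0.0 |
| 2.5, 5 (8.1) | 0.4 / 0.3 / 0.2 / 0.0 / 0.0 | 1.4 / 1.1 / 0.8 / 0.2 / 0.0 |
| 4, 3 (8.0) | 0.8 / 0.7 / 0.4 / 0.05 / 0.0 | 4.1 / 3.6 / 2.9 / 1.4 / 0.2 |
| 4, 5 (10.1) | 0.7 / 0.6 / 0.4 / 0.0 / 0.0 | 3.6 / 3.1 / 2.5 / 1.2 / 0.1 |
| 6, 5 (12.6) | 0.9 / 0.7 / 0.5 / 0.1 / 0.0 | 6.9 / 6.1 / 5.1 / 2.9 / 0.7 |

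The first three rows match Protocol 4.3; the last two assume longer survival. Scenario (b) is an upper bound. Dropping the subject and censoring at time 0 gave the same estimate.

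- **Standard error (Greenwood)** of 12-month OS: 4.9 to 6.7 points across the first three rows.
- **Loss before progression**, assumed 5% to 10%, F = 24, first three rows: 0.2 to 0.4 points if the last form was up to 12 weeks before loss; 0.6 to 2.1 with no form.
- **Date order in (a):** 41 to 65% of progression-free subjects at F = 0 to 6 have OS censored before their last scan. This share depends on the assumed form timing.
- **With a dated record from any source within 4 weeks of cutoff**, first three rows: a residual fall of 0.1 to 0.3 points at F = 0 to 6, and 0.0 from F = 12.

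A separate model checked the no-form case: n = 80, 20% of PFS events are deaths, median PFS/PPS of 3/4 or 5/5 months. At 1 month minimum follow-up, 12-month OS fell from 0.265 to 0.243 (2.2 points) or from 0.440 to 0.386 (5.4 points). At 24 months the fall was at most 0.4 points. Direction and rough size agree.

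**The case against.** The strongest reply is that the problem exists only if the form is not completed before progression. That depends on CRF v6.0, which the SAP says to read alongside it and which is not among the documents. Nothing says the Survival Status form is the record of the post-progression contact or is limited to it.

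Some text points the other way. Deaths are taken from the form, and Table 1 needs deaths without progression ("but death reported within 2 scan intervals following last adequate tumor assessment"). Protocol 14.2.1 lists survival follow-up among data for virtual visits under COVID-19 measures, next to drug compliance, which is an on-treatment item. Protocol 6.7.2 asks for End of Treatment investigations if the trial stops early, although the 9.2.7 list does not include survival status. The SAP also does not expressly exclude other sources; the form is simply the only one named.

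It is also fair to say that the effect is below the standard error and that the larger figures need assumptions no document supports: no form at all, longer survival, or an early cutoff. SAP section 3 mentions early closure only to explain limited PK data, and no cutoff date is given.

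All of this stands, and it limits the point to a minor one. It does not remove it. If the form is completed for everyone, the added sentence changes little or nothing. If it is not, programmers would either follow a rule that discards known follow-up or depart from the named source, and SAP section 2 requires such departures to be documented in the CSR.

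**Conclusion.** The point holds as a minor one. The written OS rule is narrower than the data collected and permits an OS censoring date earlier than the PFS censoring date. It is not shown that any date will actually be missing.

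For subjects progression-free at cutoff, the effect at the planned 2-year follow-up is about zero. With median OS near the protocol's 5 to 8 months, it could show only at an early cutoff, and every figure is below the standard error of the 12-month estimate. Loss before progression could add up to about 2 points at the planned follow-up, if 10% are lost and none has a form. These sizes rest on the assumed sample size, accrual, exponential survival and form timing. The direction, a lower OS estimate, does not depend on the particular values chosen.

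**What to change.** In SAP 7.3.5, define the last known alive date as the latest date on or before data cutoff at which any collected record shows the subject alive: dose, visit, laboratory sample, vital signs, scan, adverse event onset, quality-of-life questionnaire or survival contact. Use recorded dates only, not dates imputed under SAP 8.1.1. Add a programming check that no subject's OS censoring date is earlier than the PFS censoring date.

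The cost is one sentence and one check. The dates are already collected, so no new data and no protocol amendment are needed. The gain is smaller for progression-free subjects who are off treatment, because they are seen only every 8 or 12 weeks.
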